10.5 Subject Compliance Monitoring

Subjects will receive one treatment with the SCE.

Follow-up visits will be scheduled 1, 3, 6, 9, 12, and 24 months (\pm 5 days) after treatment for clinical assessments and laboratory tests as described in Section 4.2. A telephone follow-up will be performed the day after the cell infusion.

10.6 Prior and Concomitant Therapy

All T1D subjects receive their daily insulin injections prior to or during the study. Their daily insulin doses will be adjusted after receiving the SCE therapy by their own physicians, not the study PI. There will be no other new diabetes medicines or therapies will be permitted during this study.

10.7 Packaging

The SCEs will be packaged in box (4 devices/box) and shipped to the GMP facility NYBC, with the Good Manufacturing Practices (GMP) Labeling System.

After treatment with the SCE, the Final Product will be shipped to clinical site at Hackensack University Medical Center in a sterilized cooler.

10.8 Blinding

In this single-arm study, all subjects will receive open label treatment with the SCE.

10.9 Receiving, Storage, Dispensing and Return

10.9.1 Receipt of Devices

Upon receipt of the study treatment supplies, an inventory must be performed and a device receipt log filled out and signed by the person accepting the shipment. It is important that the designated study staff counts and verifies that the shipment contains all the items noted in the shipment inventory. Any damaged or unusable study device in a given shipment will be documented in the study files. The investigator must notify study sponsor of any damaged or unusable study treatments that were supplied to the investigator's site.

10.9.2 Storage

The devices are stored at the room temperature in dark cabinets of Class 100K clean room (or GMP facility for cell cultures). There is no need for protection from light. Storage considerations include avoiding dropping of the devices or placing heavy weight on top of the devices.

10.9.3 Dispensing of Study Device

All empty devices (without stem cells) are in the same quality. Any single device will be assigned to any single subject and dispensed. The only standard will be the quality of CB-SCs cultured in the device. If cell density reaches the $\geq 80\%$ of confluence, endotoxin level <0.5 EU/mL, the device with CB-SCs can be assigned to subject and prepared for clinical application.

Regular study device reconciliation will be performed to document device assignments, devices used, devices remaining, and inadvertently damaged devices. This reconciliation will be logged on the device accountability form, and signed and dated by the study team.

10.9.4 Return or Destruction of Study Device

Devices are discarded at the conclusion of the treatment as per institutional biohazard waste disposal SOP. At the completion of the study, there will be a final reconciliation of devices shipped, devices consumed, and devices remaining. This reconciliation will be logged on the device reconciliation form, signed and dated. Any discrepancies noted will be investigated, resolved, and documented prior to return or destruction of unused study devices. Any devices destroyed on site will be documented in the study files.

11 Study Procedures

11.1 Visit 1

Visits to the John Theurer Cancer Center will be as outlined in this study. The investigators will not be adjusting the participants' insulin or other diabetic medications, with the following exceptions:

- 1) If medically necessary while the participant is physically present at the JTCC during a scheduled visit.
- 2) On the day of apheresis
- 3) On the day of re-infusion.
- 4) If one of the co-investigators is the primary endocrinologist for one of the participants.
- 5) In case of emergency or if the participant is unable to contact their primary treating physician.

Screen for Enrollment: First, all consented subjects will be screened for enrollment in accordance with the Inclusion Criteria and Exclusion Criteria of SCE therapy. Patients will be qualified for enrollment if they meet the 2015 diagnosis standards of the American Diabetes Association and a blood test confirm the presence of at least one autoantibody to pancreatic islet beta cells. Depending on age, either the adult endocrinologist ([name]) or pediatric endocrinologist ([name], for patients aged from 18 to 22 years old) will review pre-procedure blood sugar logs. Respective MD would be accessible by medical team for any questions during visit regarding blood sugars. Patients will be provided additional blood sugar logs for the duration of the study. We will ask the patient to check their blood sugars at least 4 times daily and twice a week overnight. We will also give option to obtain a cloud-based glucometer (e.g., Accucheck Aviva Connect). This meter is a cloud-based meter and has a physician portal so MD can review blood sugars remotely as weekly. We can also recommend that the patient obtain a CGMS (continuous glucose monitoring system) unit to help monitor blood sugars more closely. The visit must be completed within 30 days prior to the cord blood order from cord blood bank.

- 1) CBC with different immune cell markers
- 2) Complete chemistry
- 3) EKG
- 4) Venous assessment done by an apheresis nurse. Patients without sufficient venous access will be deferred. Patients with acceptable venous access at the time of screening but who fail to collect peripherally

on the day of apheresis may have an apheresis catheter placed femorally by a surgeon for the purpose of the collection.

- 5) Autoantibody testing (see Table 3).
- 6) Infectious disease testing (HIV, HTLV, Hep B, cAB, Hep C ab.)

11.2 Visit 2

Women of childbearing potential will require a serum pregnancy test between day -7 and day -1.

The Mixed Meal Tolerance Test (MMTT): MMTT testing should be done in the morning while the subject is fasting. Subjects will be nothing by mouth (NPO) after midnight except water. Liquids that contain only simple sugars can be used to treat or prevent hypoglycemia during the night and morning prior to study. The target glucose level at the start of the test should be between 70 and 200 mg/dL for subjects with T1DM.

Insulin Application: Subjects with T1DM should take their usual dose of insulin on the evening before the test. Subjects on Lantus or Levemir should take their usual injection the evening before and/or on the morning of the test, as per their normal routine. Subjects on CSII should continue with their usual basal settings on night prior to test. Usual doses of rapid-acting insulin analog will be used until midnight the evening before the test. Small correction doses of rapid-acting insulin analog may also be used up to 4 hours before the test if needed to achieve a blood glucose level <150 mg/dL at the start of the study. Usual doses of NPH insulin and rapid-acting insulin analogs are not given on the morning of the test.

Blood Sampling: Blood will be obtained for measurement of plasma glucose, c-peptide and glucagon at -10, 0, 15, 30, 60, 90, 120, 150 and 180 minutes. A split-duplicate sample for quality control will also be collected. IV lines will be inserted in one arm for blood sampling.

Boost Dose: The mixed meal used will be Boost High Protein Gluten Free Drink with 20g of sugar per bottle. The MMTT should take 180 minutes to perform. The dose of Boost High Protein Gluten Free Drink with 20g of sugar per bottle, given at time 0 minutes. The dose should be consumed in no more than 5 minutes.

11.3 Visit 3

Patients will undergo leukapheresis. Adult endocrinologist or Pediatric Endocrinologist to be on-call for questions.

11.4 Visit 4

Infusion of the cellular product after exposure to the SCE. Adult endocrinologist or Pediatric Endocrinologist to be on-call for questions.

The cellular product will be released based on the results of a Gram stain and endotoxin test, with results of sterility available after the 14 day sterility test. If the tests reveal a sterility failure and there are any signs (e.g., fever, vomiting, and increased CBC count) of infection in subjects after infusion, the management and handling will be performed according to our standard SOPs at HackensackUMC, "Name of Procedure: Management and Handling of Cellular Products with Positive Microbial Cultures". Antibiotics need to be administered in the event that microbial contamination is present in the product that the subject already received. The route (oral or i.v.) and dosage of administering antibiotics will be determined according to the type of infection. To identify the microorganism(s), anti-microbial agent sensitivity testing needs to be performed during the sterility test. If the subject experiences any serious and unexpected adverse reaction that could be from administration of a non-sterile cellular product, then the endocrinologist must report this information to the FDA in an IND safety report no more than 15 calendar days after the initial receipt of the information. The endocrinologist must also report the sterility failure, results of investigation of cause and any corrective actions, in an information amendment submitted to the IND within 30 calendar days after

initial receipt of the positive culture test result. All these reports will be handled according to our SOPs at HackensackUMC, "Name of Procedure: Biological Product Deviation" and "Name of Procedure: Incidents, Errors, Accidents, Deviations, Variances and Complaints Reporting".

To determine which step caused contamination and to prevent sterility lapses in the future, all procedures will be fully examined from the collection of the cord blood unit, all steps of Operations, the isolation of mononuclear cells (MNCs) by apheresis, and to the packing and shipping of final product between the clinical site and the GMP facility. If the reagents and materials are contaminated, they will be discarded. New reagents and materials will be used for the production of Stem Cell Educators (SCE) and SCE-treated MNCs.

11.5 Visit 5

Safety Phone Call Day + 1 to + 2 after the re-infusion.

11.6 Visit 6

Safety visit 7 days \pm 1 day after the re-infusion.

11.7 Visit 7

Follow-up visit 1: It is scheduled 1 month (\pm 5 days) after treatment for clinical assessments and laboratory tests as per Section 3.2, Table 3. To be reviewed by respective Endocrinologist.

11.8 Visit 8

Follow-up visit 2: It is scheduled 3 months (\pm 5 days) after treatment for clinical assessment (e.g., fasting blood glucose, C-peptide, and HbA1C) and laboratory tests as per Section 3.2, Table 3. To be reviewed by respective Endocrinologist.

11.9 Visit 9

Follow-up visit 3: It is scheduled 6 months (\pm 5 days) after treatment for clinical assessment (e.g., fasting blood glucose, C-peptide, and HbA1C) and laboratory tests as per Section 3.2, Table 3. To be reviewed by respective Endocrinologist.

11.10 Visit 10

Follow-up visit 4: It is scheduled 9 months (\pm 5 days) after treatment for clinical assessment (e.g., fasting blood glucose, C-peptide, and HbA1C) and laboratory tests as per Section 3.2, Table 3. To be reviewed by respective Endocrinologist.

11.11 Visit 11

Follow-up visit 5: It is scheduled 12 months (\pm 5 days) after treatment for clinical assessment (e.g., fasting blood glucose, C-peptide, and HbA1C) and laboratory tests as per Section 3.2, Table 3. To be reviewed by respective Endocrinologist.

11.12 Visit 12

Follow-up visit 6: It is scheduled 24 months (\pm 5 days) after treatment for clinical assessment (e.g., fasting blood glucose, C-peptide, and HbA1C) and laboratory tests as per Section 3.2, Table 3. To be reviewed by respective Endocrinologist.

12 Statistical Plan

12.1 Statistical Methods

This is a prospective, single-arm, open-label, single-center study to assess the safety, feasibility, and efficacy of SCE therapy for the treatment of patients with T1D. Ten patients meeting eligibility criteria will be enrolled for this study, with an effect size of 0.8 ng/mL at a 0.025 significance level and 80% power. All patients will be included in the safety analyses. The primary safety analysis will be performed in the safety population. The occurrences of treatment-related adverse events will be evaluated and presented as counts (percentages) and binomial 95% exact binomial confidence intervals (CI).

The feasibility of the SCE therapy will be assessed by analyzing the number of the patients unable to complete the therapy and the number of patients who are lost to follow-up prior to the 12-month visit. Both of these parameters will be analyzed as counts (percentages) and corresponding 95% CI as described in the safety analysis section above.

Statistical analyses of data will be performed by *t*-test using Power and Precision software (www.power-analysis.com). The paired *t* test will be used to study the significance between baseline and follow-ups. Using the fasting blood glucose levels and the plasma C-peptide, as well as their levels following OGTT or MMTT as the parameters, we want to detect the difference after the SCE therapy with an effect size of 0.8 ng/mL at 2.5% significance level, 80% power, and one side. According to our calculations, we will need 10 subjects in order to find this difference.

Area under the C-peptide curve will be calculated with C-peptide level measured at 0, 30, 60, 90, 120, 150 and 180 minutes of the MMTT using the trapezoid rule. The AUC for C-peptide over 120 minutes of the MMTT will be evaluated and summarized using descriptive stats mean (SD) or median (IQR), as appropriate. This calculation will be obtained for each of the time points, baseline, 3, 6, 9, 12, and 24 months and longitudinal analysis will be performed to evaluate the changes over time. This analysis of changes over the time points will be achieved using mixed effect models for repeated measures (MMRM) implemented using PROC MIXED in SAS version 9.4. As this is a secondary analysis no adjustment for multiple test will be employed for this analysis.

Mean AUC for C-peptide over 3 hour MMTT, which is defined as the AUC divided by the duration of the test i.e., 180 minutes, will be calculated at baseline, and all subsequent post-baseline points, and changes over time will be analyzed using MMRM method as defined in the AUC for C-peptide subsection above.

HbA1C levels assessed at baseline, 3, 6, 9, 12, and 24 months will be summarized using descriptive statistics at each time point. To evaluate changes in HbA1C levels assessed at baseline and post-baseline time points, the MMRM analysis defined in AUC for C-peptide will be performed.

All study data will be entered into a Microsoft Office Excel 2013 (Microsoft Corporation, Redmond, WA) and imported into SAS 9.4. The database will be validated in SAS to ensure any out of range values are queried for all multiple source until all data issues are resolved. Any $p < 0.05$ will be considered statistically significant. All data analysis will be performed using SAS version 9.4 (SAS Institute Inc. Cary, NC).

Stopping rule: If a grade 3 adverse event, as per the Common Terminology Criteria for Adverse Events (CTCAE) Version 4.0, related to the study procedure occurs in 2 patients, the study will be terminated.

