8.2 Primary Study Endpoint

The primary study endpoint will be the occurrence of treatment-related adverse effects. Adverse events that occur during therapy (especially those that necessitate temporary or permanent discontinuation of therapy) and over the 12-month follow-up period will be assessed.

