13.1.2 Adverse Event

An **adverse event** (AE) is any symptom, sign, illness or experience that develops or worsens in severity during the course of the study. Concurrent illnesses or injuries should be regarded as adverse events. Abnormal results of diagnostic procedures are considered to be adverse events if the abnormality:

- results in study withdrawal
- is associated with a serious adverse event
- is associated with clinical signs or symptoms
- leads to additional treatment or to further diagnostic tests
- is considered by the investigator to be of clinical significance

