13.2 Recording of Adverse Events

Based on our current clinical data in 200 subjects including Chinese and Caucasian patients, we did not see any significant adverse events during the treatment with SCE therapy, and follow-up studies after treatment for 4 years. No participants experienced any significant adverse events during the course of treatment. Most patients experienced mild discomfort during venipuncture and some soreness of the arm during aphaeresis, but discomfort and soreness resolved quickly following the conclusion of the procedure. No tumor formation and other safety concerns in all subjects after receiving SCE for 4 years.

At each contact with the subject, the investigator must seek information on adverse events by specific questioning and, as appropriate, by examination. Information on all adverse events should be recorded immediately in the source document, and also in the appropriate adverse event module of the case report form (CRF). All clearly related signs, symptoms, and abnormal diagnostic procedures results should be recorded in the source document, though should be grouped under one diagnosis.

All adverse events occurring during the study period must be recorded. The clinical course of each event should be followed until resolution, stabilization, or until it has been determined that the study treatment or participation is not the cause. Serious adverse events that are still ongoing at the end of the study period must be followed up to determine the final outcome. Any serious adverse event that occurs after the study period and is considered to be possibly related to the study treatment or study participation should be recorded and reported immediately.

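### Section 12 specifies no all-cause adverse-event or serious-adverse-event summary beside the treatment-related rate, so in this open-label single-arm trial the reported safety result rests on attribution that cannot be checked

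*Combined protocol and SAP*

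**What the plan says.** Section 8.2 defines the endpoint: "The primary study endpoint will be the occurrence of treatment-related adverse effects". Its next sentence concerns adverse events during therapy, without a relatedness condition, and ends "and over the 12-month follow-up period will be assessed". It names no statistic.

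Section 12.1 gives the one adverse-event analysis: "The occurrences of treatment-related adverse events will be evaluated and presented as counts (percentages) and binomial 95% exact binomial confidence intervals (CI". Section 12.2 adds that everyone who received treatment enters the safety analyses.

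Elsewhere the net is wider. Section 13.1.2 defines an adverse event broadly: "Concurrent illnesses or injuries should be regarded as adverse events". Section 13.2 requires capture without regard to cause: "All adverse events occurring during the study period must be recorded". Section 13.5.1 has the DSMB look at how often AEs and SAEs occur and how severe they are. Section 13.5 has a medical monitor review SAEs and unanticipated problems.

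Section 10.8 describes the setting: "In this single-arm study, all subjects will receive open label treatment with the SCE".

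The stopping rule in Section 12.1, repeated in Section 13.4, counts grade 3 events with a different label: "related to the study procedure occurs in 2 patients, the study will be terminated".

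**The concern.** Calling an event treatment-related is a judgement. In a randomised trial a comparator rate puts a limit on how far that judgement can mislead. Here there is no comparator and no blinding, so nothing in the data can show whether related events were under-called or over-called. A count of patients with any event avoids this filter, and Section 12 does not ask for one.

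The plan also leaves the judgement loosely specified. Section 13.3 lists the investigator's assessment of association among the items of a narrative report for reportable events. No causality scale is given, and no assessor is named for non-serious events. The endpoint and the stopping count use two different attribution terms, and neither is defined.

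At stake is the answer to the primary objective. A final report that follows Section 12.1 to the letter could show a very low related-event rate and no pre-specified figure to set beside it.

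**Working it through.** **1. Which events each section covers**

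| Section | Events covered | Statistic specified |
|---|---|---|
| 8.2, first sentence | treatment-related | none (defines the endpoint) |
| 8.2, second sentence | AEs in therapy and over 12 months, no filter | none |
| 12.1 | treatment-related | count, percentage, exact 95% CI |
| 12.1 and 13.4, stopping rule | grade 3, related to the study procedure | number of patients |
| 13.2 | all AEs | none (recording) |
| 13.5 | SAEs, unanticipated problems | none (medical monitor review) |
| 13.5.1 | AEs and SAEs, no filter | none for the final analysis (DSMB oversight) |

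Only the treatment-related row carries an estimate with an interval.

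**2. The plan's own figure.** There is none to reproduce. The plan states no safety rate, threshold or precision target. The 10 subjects come from the C-peptide calculation in Section 12.1 and serve here only as the denominator.

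**3. How far apart the two displays can be.** The exact (Clopper-Pearson) 95% limits for x patients out of n are:

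- lower = 0.025 quantile of Beta(x, n − x + 1), or 0 if x = 0
- upper = 0.975 quantile of Beta(x + 1, n − x)

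For x = 0 and n = 10 the upper limit is 1 − 0.025^(1/10) = 30.8%. The event counts below are assumed for illustration.

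| Patients with an event | Rate | Exact 95% CI |
|---|---|---|
| 0/10 | 0% | 0 to 30.8% |
| 2/10 | 20% | 2.5 to 55.6% |
| 4/10 | 40% | 12.2 to 73.8% |

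If four patients have an event and two of those are judged related, Section 12.1 reports the 20% line. If none is judged related, it reports the 0% line. The 40% line appears in neither case.

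**4. Sensitivity to attribution.** Let p be the per-patient risk of an event that the treatment really causes, and s the chance that it is called related. The documents give neither, so both are assumed. Patients are taken as independent, with no false attribution. The chance of no related event in 10 patients is (1 − p·s)^10.

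| p | s = 1 | s = 0.75 | s = 0.5 | s = 0.25 |
|---|---|---|---|---|
| 10% | 34.9% | 45.9% | 59.9% | 77.6% |
| 20% | 10.7% | 19.7% | 34.9% | 59.9% |
| 30% | 2.8% | 7.8% | 19.7% | 45.9% |

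At p = 30%, for example, 0.70^10 = 2.8% with full attribution and 0.85^10 = 19.7% when half are attributed.

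The stopping count depends on attribution in the same way. Write q = p·s and read p as the risk of a procedure-caused grade 3 event. The chance of two or more patients in 10 is then 1 − (1 − q)^10 − 10q(1 − q)^9. At p = 30% it falls from 85.1% (s = 1) to 45.6% (s = 0.5) and 17.0% (s = 0.25). At p = 20% it falls from 62.4% to 26.4% and 8.6%.

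**The case against.** The strongest reply is that all-cause events are not neglected. They are defined broadly, recorded, assessed over 12 months under Section 8.2 and reviewed by the DSMB without a relatedness filter, and SAEs have a second reader in the medical monitor. This stands. A reader who infers from Section 12 that all-cause events are never looked at goes beyond the documents. What it leaves open is narrower: recording and oversight are not a specified analysis, and Section 8.2 gives no method for its assessment.

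A second reply is that a related-event endpoint is common in an early single-arm pilot, and that an any-cause rate is hard to interpret. Section 13.1.2 counts concurrent illness, so over 12 months many of ten patients could qualify for reasons unrelated to therapy. This also stands. It is a good reason to keep the endpoint and not replace it, but no reason to omit the companion summary.

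A third reply concerns the two attribution terms. One might infer that an apheresis or catheter harm could count as procedure-related yet escape the treatment-related endpoint. The documents do not support that. Sections 8.1 and 10.2 make apheresis part of the treatment, and Table 3 lists it in the treatment block with the infusion. The terms still differ and are undefined, so they need reconciling, but no such gap is established.

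One might also infer that the interval is invalid because it is placed on events. Section 12.1 works in the safety population and applies the same method to numbers of patients in its next paragraph, so patients are the natural unit. A word of clarification is enough.

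Finally, Section 13.2 reports of earlier subjects that "we did not see any significant adverse events during the treatment with SCE therapy". To read this as having biased the assessors would be conjecture.

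**Conclusion.** The point holds in this form: Section 12 analyses treatment-related events only and specifies no all-cause AE or SAE summary, in a design where attribution cannot be checked. The primary safety rate is therefore incomplete as planned, although the endpoint itself is defensible.

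The size depends on events not yet seen. With ten treated patients and the assumed counts, a reported 0% (0 to 30.8%) could coexist with 40% (12.2 to 73.8%) of any cause. If the true risk of a treatment-caused event were 30%, the chance of a clean related-event result would rise from 2.8% with full attribution to 19.7% with half. These figures show sensitivity and are not a forecast. Nothing in the documents indicates that attribution will in fact be poor.

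The change is worth making because the primary objective depends on it and most of the data are already called for.

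**What to change.** - **Section 12.1, beside the related-event result and at equal prominence.** Add the number and percentage of treated patients with at least one AE, and with at least one SAE, of any cause. Count from the start of apheresis through the 12-month follow-up in Section 8.2, by worst CTCAE grade, with exact 95% CIs. State that the unit is the patient. Since Section 10.2 makes apheresis part of treatment, say that a patient who starts apheresis but is not infused is in the denominator.
- **Related events.** Keep the treatment-related endpoint. Tabulate its events by component: apheresis or catheter, cell product, infusion.
- **Attribution term.** Reconcile the wording in Sections 8.2 and 12.1 with that of the stopping rule in Sections 12.1 and 13.4, using one stated definition of related that says what it covers and who applies it. This asks for consistent terms only. The content of the stopping rule is for the sponsor.
- **Window.** Section 13.1.4 ends the reporting period 30 days after treatment, while Section 8.2 assesses events over 12 months. These must be reconciled, or the new table has no agreed end.

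**Cost.** One or two extra tables and edits to a few sections, with no change in sample size. No extra data collection is needed if AEs are captured over the 12 months that Section 8.2 implies. The all-cause rate will look less favourable and will include unrelated illness, so the report should say so.

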8.3.2 Efficacy endpoints

- 8.3.2.1 Area under the C-peptide curve (AUC) over the first 2 hours of a 3-hour mixed meal tolerance test (MMTT). The AUC at 12-months and changes over time will be assessed.
- 8.3.2.2 Peak C-peptide levels over a 3-hour MMTT. The peak C-peptide level at 12-months and changes over time will be assessed.
- 8.3.2.3 Basal C-peptide levels at 12-months and changes over time will be assessed.
- 8.3.2.4 Daily insulin requirements
- 8.3.2.5 Change in HbA1C levels over time
- 8.3.2.6 Changes in auto-antibody levels over time

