9.4.2 Data Collection and Follow-up for Withdrawn Subjects

Even though subjects may be withdrawn prematurely from the study, it is imperative to collect toxicity data for 12 weeks after. We will use all possible methods (e.g. number of phone calls to subject, phone calls to health care proxy, if possible, certified letters, etc.) to confirm that the subject is truly lost for follow-up. If a patient withdraws from the study prior to their 12 month follow-up, enrollment of a replacement patient will occur.

10 Study Device

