12.2 Subject Population(s) for Analysis

All subjects who received treatment will be included in the safety analyses. The primary efficacy end point will be the change in C-peptide secretion between baseline and follow-up.

13 Safety and Adverse Events

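### Section 12.1 attaches one power claim (10 subjects, 0.8 ng/mL, one-sided 2.5%, 80%) to both glucose and C-peptide: it is wrong for glucose, and for C-peptide it rests on an SD that Section 12.1 neither states nor cites

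*Combined protocol and SAP*

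**What the plan says.** Section 12.1 makes the claim twice. Its opening paragraph sets ten patients "with an effect size of 0.8 ng/mL at a 0.025 significance level and 80% power", without saying whether the test is one- or two-sided. A later paragraph names the paired t-test and lists the variables: "Using the fasting blood glucose levels and the plasma C-peptide, as well as their levels following OGTT or MMTT as the parameters". It then repeats the claim, "with an effect size of 0.8 ng/mL at 2.5% significance level, 80% power, and one side", and concludes that ten subjects are needed. It refers to the authors' own calculations and names the software, but gives no SD, no correlation between visits and no source for either.

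Other places bear on the reading:

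- Section 8.3.2 lists three C-peptide measures. For the 2-hour MMTT curve it says "The AUC at 12-months and changes over time will be assessed", and for the fasting value "Basal C-peptide levels at 12-months and changes over time will be assessed". Peak C-peptide is treated in the same way.
- Section 12.1 also defines a 3-hour mean AUC, "which is defined as the AUC divided by the duration of the test i.e., 180 minutes", and analyses changes in AUC and mean AUC with a mixed model for repeated measures (MMRM).
- Section 12.2 says "The primary efficacy end point will be the change in C-peptide secretion between baseline and follow-up", without choosing among these measures.
- Section 11.2 gives glucose in mg/dL. Section 10.3 gives C-peptide in ng/mL.
- Table 3 schedules the MMTT and no OGTT.
- Section 8.2 makes treatment-related adverse events the primary endpoint. Section 7.2 places preliminary efficacy among the secondary objectives.

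**The concern.** One effect, in one unit, is claimed for two analytes whose scales differ by orders of magnitude. A difference in ng/mL is natural for C-peptide and meaningless for glucose. A unit-free effect could serve both, but then the sample size can be checked from the stated inputs alone.

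A printed 80% affects how results are read. In Section 12.1 it is the only quantitative basis for ten subjects. If the real power for C-peptide could lie anywhere from below one half to nearly certain, a reader cannot tell whether a non-significant change is evidence against an effect or merely a lack of information. The claim also fixes no single C-peptide measure, and 0.8 ng/mL cannot apply to the trapezoid AUC, whose unit is ng/mL × min.

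**Working it through.** **Inputs.** From Section 12.1: n = 10, paired t-test, one-sided α = 0.025, target power 80%, effect 0.8 ng/mL. The SD of the within-patient change is not given there, so the values used below are assumptions.

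**Formula.** With δ the mean change and SD the standard deviation of the change, power = 1 − F(t₁₋α,ₙ₋₁), where F is the noncentral t distribution function with n − 1 degrees of freedom and noncentrality (δ/SD)√n. For n = 10 the critical value is 2.262.

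**Reproducing the plan's ten.** It cannot be reproduced without an SD. Solving for 80% power at n = 10 gives δ/SD = 0.996, so SD = 0.8/0.996 = 0.803 ng/mL. An SD of about 0.75 to 0.80 returns exactly ten subjects.

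**Reading 1: raw 0.8 ng/mL, glucose.** 0.8 ng/mL × 100 mL/dL = 80 ng/dL = 0.00008 mg/dL. For 80% power the SD of change would have to be 0.00008 mg/dL or less. At an assumed SD anywhere from 1 to 40 mg/dL, power is 2.5%, which is α.

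**Reading 2: raw 0.8 ng/mL, C-peptide.**

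| Assumed SD of change (ng/mL) | Power at n = 10 | n for 80% |
|---|---|---|
| 0.6 | 96% | 7 |
| 0.7 | 89% | 9 |
| 0.8 | 80% | 10 |
| 0.9 | 71% | 12 |
| 1.0 | 62% | 15 |
| 1.2 | 47% | 20 |

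**Reading 3: standardised effect of 0.8.** Noncentrality = 0.8 × √10 = 2.530. Power is 61.6% at n = 10, 79.0% at n = 14 and 82.1% at n = 15, so 80% needs 15. Section 12.1 also uses a general threshold of p < 0.05. Taken as two-sided, it leaves power at 61.6%; taken as one-sided, it gives 75.4%.

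**Choice of measure.** Basal C-peptide, peak C-peptide and a time-averaged AUC are in ng/mL. The raw 2-hour AUC is not: a 0.8 ng/mL change in the 2-hour average is 0.8 × 120 = 96 ng/mL × min. The 2-hour AUC must be divided by 120 minutes. Dividing it by the full 180-minute test would give 120/180, or two thirds, of the correct mean.

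**Numbers for the replacement text.** At one-sided 2.5%, a change of 1.0 SD has 80.3% power with ten pairs and 68% with eight; a change of 0.8 SD has 61.6% with ten pairs. For safety, 0 events in 10 has an exact 95% upper limit of 1 − 0.025^(1/10) = 30.8%. The chance of at least one event at a true rate of 15% is 1 − 0.85¹⁰ = 80.3%.

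**The case against.** The best defence is that the unit settles the matter. Throughout the protocol ng/mL is the C-peptide unit, Section 12.2 names C-peptide as the main efficacy variable, and glucose in the list is loose drafting. On that reading the calculation contains no demonstrated error, only an undocumented input. This stands for C-peptide. It does not rescue the sentence, which names glucose expressly.

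A second defence is that ten can be recovered from a standardised 0.8 with the normal approximation at one-sided 5%: ((1.645 + 0.842)/0.8)² = 9.66, rounded up to 10. That may be where the figure came from, but it contradicts both the stated 2.5% and the stated t-test.

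Third, an SD may exist elsewhere. Parts of the clinical background in Section 6.4 were not available for this review, and the C-peptide results in Section 6.4.2.4 break off. The finding is therefore limited to what Section 12.1 states or cites. The nearest available SDs are 0.19 and 0.33 ng/mL in Section 6.4.3.2, for fasting C-peptide in seven type 2 patients at single time points. With an assumed correlation of 0 to 0.75 they give an SD of change of 0.38 to 0.23 ng/mL and a sample size of 5 to 3. They do not explain ten, and Section 12.1 does not refer to them.

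Finally, this is a single-arm pilot with a safety endpoint, and a confidence interval will show what the C-peptide data can exclude. That limits the consequence, but a false power figure for a named variable should still be corrected.

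A reader might infer that the trial is underpowered for C-peptide and needs 15 subjects. The documents do not support this: 15 follows only if the printed unit is discarded, or if the SD of change is about 1.0 ng/mL.

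**Conclusion.** The power claim is wrong as written for glucose, where power is 2.5% rather than 80%. As a standardised effect it also fails: 61.6% at ten subjects, with 15 needed. For C-peptide in ng/mL it is unsupported but not shown to be wrong. It is true if the SD of within-patient change is at most about 0.80 ng/mL, and power runs from 96% to 47% over assumed SDs of 0.6 to 1.2. These figures assume the stated one-sided 2.5% paired t-test with ten complete pairs and roughly normal changes.

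The effect is confined to the efficacy power statement. It does not touch the primary safety endpoint or show that ten is the wrong size for a pilot. It should be corrected because a printed 80% invites over-reading of a null C-peptide result and correction is cheap.

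**What to change.** Keep ten subjects. Delete glucose from the power statement, and delete the OGTT because Table 3 schedules only the MMTT. Replace both power sentences with:

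> For the change from baseline to month 12 in [one named C-peptide measure in ng/mL: basal, peak, or 2-hour AUC divided by 120 minutes], a one-sided 2.5% paired t-test with 10 evaluable pairs has 80% power for a mean change of about 1.0 SD of the within-patient change and 62% for 0.8 SD (68% for 1.0 SD with 8 pairs).

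Express the detectable change in ng/mL only with a cited SD of change. If an AUC measure is chosen, add that the paired t-test is the basis for the power figure, while Section 12.1 analyses AUC by MMRM.

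The eight-pair figure is there because ten pairs are not assured. Section 9.4.2 says "If a patient withdraws from the study prior to their 12 month follow-up, enrollment of a replacement patient will occur", but Sections 8.1 and 9 cap enrolment at ten, and replacement does not cover a missed or unusable month-12 test.

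Alternatively, drop the power claim and state the precision for the primary endpoint: with 0 of 10 patients having a given treatment-related event, the exact 95% interval is 0 to 30.8%, and there is an 80% chance of seeing at least one event if the true rate is 15%. This matches the exact binomial interval already planned.

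The cost is protocol wording only, with no extra patients, visits or samples. The downside is that an unconditional 80% becomes conditional. Under the first option, the sponsor must also commit to one C-peptide measure.
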